#### 6.1.8. Data Adjustments/Handling/Conventions

All collected data will be presented in listings. Data not subject to analysis according to this plan will not appear in any tables or graphs but will be included only in the data listings.

All *P* values will be displayed in four decimals and rounded using standard scientific notation (e.g., 0.XXXX). If a *P* value less than 0.0001 occurs it will be shown in tables as <0.0001; similarly, if a *P* value greater than 0.9999 occurs it will be shown in tables as >0.9999.

Adverse events will be coded using the Medical Dictionary for Regulatory Activities (MedDRA) version 23.0 thesaurus.

Medications will be coded using the World Health Organization Drug Dictionary Enhanced (WHO-DDE) Global B3 version September 2019.

A treatment-related AE is any AE with a relationship to the study drug of possibly related, probably related, likely related, or missing.

For partial AE and medication start dates:

- If the year is unknown, then do not impute the date but assign a missing value.
- If the year is known, but the month or month and day is unknown, then:
  - If the year matches the year of first dose date and the end date (if present) is after first dose date, then impute as the month and day of the first dose date.
  - Otherwise, assign 01 January.

- If the year and month are known, but the day is unknown, then:
  - If the month and year match the month and year of the first dose date, then impute as the day of the first dose date.
  - Otherwise, assign 01.

For partial AE and medication end dates:

- If the year is unknown, then do not impute the date but assign as missing value.
- If the year is known, but the month or month and day is unknown, then:
  - If the year matches the year of the last date of the study (date of last contact if subject lost to follow-up; date of completion or early termination otherwise), then impute as the month and day of the last date of the study.
  - Otherwise, assign 31 December.
- If the year and month are known, but the day is unknown, then:
  - If the month and year match the month and year of the last date of the study, then impute as the day of the last date of the study.
  - Otherwise, assign the last day of the month.

These conventions will be applied to AE and medication onset dates and times with the following precaution: if the missing date and time reflect the date and time of onset of an AE, the modified date and time will be constructed to match the first documented date/time post drug administration while preserving the order in which the AE was reported in the eCRF.

In cases where variables for questionnaires were derived in the eCRF (e.g., total scores) and a derivation is indicated in [Section 6.1.7](#), the results as derived by statistics (as opposed to the results derived in the eCRF) will be used in analysis.

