4.3 Subject Participation

Phase 1 (Cohort 1)

Subject participation involves a minimum of 7 clinic visits including Screening, Baseline/Day 1, Day 2, Day 8, Day 15, Day 16 and Day 22. Subjects will be treated with investigational product (ARQ-252 cream 0.3% QD) for 2 weeks. The interval between the Screening and Baseline visits could be up to 4 weeks, therefore the anticipated maximum duration of subject participation is 7 weeks.

Phase 2b (Cohort 2)

Subject participation involves a minimum of 7 clinic visits including Screening, Baseline/Day 1, Week 2, Week 4, Week 8, Week 12 and Week 13. Subjects will be randomized to a treatment group and will be treated with investigational product for 12 weeks. The interval between the Screening and Baseline visits could be up to 4 weeks, therefore the anticipated maximum duration of subject participation is 17 weeks.

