5.7 Adverse Events

5.7.1 Adverse Event Definition

An AE means any untoward medical occurrence associated with the use of a drug in humans, whether or not considered drug related. An AE can therefore be any unfavorable and unintended sign (including an abnormal laboratory finding), symptom, or disease temporally associated with the use of a medicinal (investigational) product, whether or not related to the medicinal (investigational) product.

AEs will be collected following informed consent of the subject through subject study completion.

A treatment emergent adverse event (TEAE) is defined as an AE that started post application of investigational product through study completion.

Application site reactions will be considered adverse events if they require intervention, suspension or discontinuation of investigational product.

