- **Number of Expected IP Applications (BID dosing)** = 170 (Cohort 2 BID) for subjects who complete the study or number of days between first and last application of IP, derived as  $2 * (\text{last treatment date} - \text{first treatment date} + 1)$ , for subjects who discontinue early from the study.
- **Number of Expected IP Applications (QD dosing)** = 30 (Cohort 1) or 85 (Cohort 2 QD) for subjects who complete the study or number of days between first and last application of IP, derived as  $(\text{last treatment date} - \text{first treatment date} + 1)$ , for subjects who discontinue early from the study.
- **Number of IP Applications** = number of expected IP applications – missed IP applications as collected in the electronic case report form (eCRF).
- **Weight of IP (g)** = returned tube weight – dispensed tube weight.
- **Body Mass Index (BMI) ( $\text{kg}/\text{m}^2$ )** =  $[\text{weight (kg)} / \text{height (cm)} / \text{height (cm)}] \times 10,000$ .
- **Change from Baseline** = value at current time point – value at baseline.
- **Treatment Emergent AE (TEAE)** = any AE with an onset date/time after the first application of IP. If time is unavailable, any AE occurring on or after the date of first application of IP will be considered treatment emergent.
- **Completion of Study** = Completion of the primary efficacy assessment (IGA) at Week 12. This may differ than what was recorded in the eCRF.

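### For partial start dates with only the day missing, SAP 6.1.8 leaves out the end-date check, so a record that ended before first dose in the dosing month is given a start after its own stop

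*SAP*

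**What the plan says.** SAP 6.1.8 sets out one scheme, introduced by "For partial AE and medication start dates". Two of its branches can assign the first-dose date.

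- **Month missing, with or without the day.** The first-dose month and day are used "If the year matches the year of first dose date and the end date (if present) is after first dose date". Otherwise the start becomes 01 January.
- **Day missing, month and year known.** The first-dose day is used on one test only: "If the month and year match the month and year of the first dose date". Failing that, the start becomes the first of the month. The end date plays no part.

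The section closes with a precaution for adverse-event onsets: when onset is missing, "the modified date and time will be constructed to match the first documented date/time post drug administration". This too makes no exception for an event with a recorded end before dosing.

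SAP 6.1.7 then classifies by date: "If time is unavailable, any AE occurring on or after the date of first application of IP will be considered treatment emergent". SAP 9.7 counts a medication as prior if it started before the first application. It counts a medication as concomitant if it continues past, or starts after, that application.

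**The concern.** Giving an uncertain onset the first-dose date is a common cautious convention, and it is sensible when the true onset could lie on either side of dosing. It fails when the record carries an end date before dosing, because onset cannot then have been on or after Day 1. The SAP applies this logic when the month is missing and drops it when only the day is missing. No reason is given, which suggests an oversight.

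The case can arise. Under Protocol 5.7.1, "AEs will be collected following informed consent of the subject through subject study completion", and under Protocol 4.3, "The interval between the Screening and Baseline visits could be up to 4 weeks". Short pre-dose events can therefore be recorded in the calendar month in which dosing later starts. At stake are an event counted in the treatment-emergent tables although it ended before exposure, a medication lost from the prior-medication table, and impossible date pairs in the listings.

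**Working it through.** No stated figure needs reproducing; the check is to follow the rule literally.

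**Inputs.** The two branches and the onset precaution come from SAP 6.1.8, the treatment-emergent definition from SAP 6.1.7, the medication definitions from SAP 9.7, and the 4-week screening limit from Protocol 4.3. Calendar dates are illustrative assumptions.

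**Test records, first dose 20 August 2020.** The last column adds the missing check: use the first-dose day only if the end date is absent or not before first dose, otherwise day 01.

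| Recorded start | Recorded end | Start imputed as written | Start imputed with the check |
|---|---|---|---|
| Aug 2020, day missing | 10 Aug 2020 | 20 Aug 2020 (20 − 10 = 10 days after the end) | 01 Aug 2020 |
| Aug 2020, day missing | none | 20 Aug 2020 | 20 Aug 2020 |
| Aug 2020, day missing | 25 Aug 2020 | 20 Aug 2020 | 20 Aug 2020 |
| 2020 only | 10 Aug 2020 | 01 Jan 2020 | 01 Jan 2020 |
| Jul 2020, day missing | 10 Aug 2020 | 01 Jul 2020 | 01 Jul 2020 |

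Only the first record goes wrong, and only it changes when the check is added.

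**Classification of the first record.** As an adverse event with no onset time, a 20 August onset is on the first-application date, so SAP 6.1.7 makes it treatment-emergent. As a medication, it no longer starts before the first application, so it is not prior under SAP 9.7.

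**Enumeration.** Take every first-dose date from 1 July 2020 to 30 June 2021 (365 dates) and every start/end pair lying wholly in the 28 days before dosing (28 × 29 / 2 = 406 pairs). That gives 365 × 406 = 148,190 combinations.

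- 55,622 of them (55,622 / 148,190 = 37.5%) start in the first-dose month. With the start day missing, all 55,622 are inverted as written.
- With the check added, none is inverted.
- The month-missing branch inverts none in either case.

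The 37.5% is a share of enumerated date pairs, all with the start day assumed missing. It does not forecast how many trial records will be affected.

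**Day 01 is a safe fallback.** If a record ended before first dose within the dosing month, the first dose was on the 2nd or later. Day 01 is then both before dosing and no later than the recorded end.

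**Boundary of the problem.** If the end day is missing too, the SAP's end-date rule assigns the last day of the month, or the last study date if that falls in the same month. Such a record is not inverted, though it may appear to run past dosing. The defect needs a complete pre-dose end date.

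**The case against.** The strongest reply is that this is a narrow programming matter. Four things must coincide: a missing start day, a start in the dosing month, a complete end date, and an end before dosing. Protocol 5.7.5 asks for date and time of onset, and Protocol 7.4 provides edit checks for missing and inconsistent data before lock. Safety summaries are descriptive (SAP 9), the rule is the same in every arm, and the SAP resolves other gaps toward the worst case, for instance by treating missing relationship as related (SAP 9.1). All of this stands as an argument about size. It does not rescue the rule: worst-case imputation is for ambiguous records, and a recorded pre-dose end removes the ambiguity.

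A reader might infer more than the documents support.

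- **That the whole start-date scheme lacks the check.** It does not; the month-missing branch has it.
- **That this is the usual kind of partial date, or is bound to occur.** The documents give no counts of partial dates.
- **That washed-out eczema therapies will be caught in number.** The drug must start, not merely stop, in the dosing month. With the washouts in Protocol Table 2, that is impossible for 3 or 6 months. It needs dosing on day 29 or later for 28 days, day 15 or later for 14 days, and day 8 or later for 7 days. Therapies begun in earlier months take the day-01 fallback and are handled correctly.
- **That such a drug becomes concomitant and looks prohibited.** SAP 9.7 requires continuing or starting after the first application, and a Day 1 start with an earlier stop plainly meets neither. The Listing 16.2.9.7 footnote, which refers to starting during the treatment period, can be read the other way. Status is therefore ambiguous. Nothing in the documents derives protocol deviations from imputed dates, and that listing shows the end date.

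**Conclusion.** The point holds for the day-missing branch only. Followed literally, it gives a start after the recorded stop for any record with a dosing-month start, a missing start day and a complete pre-dose end. An adverse event of this kind with no onset time is wrongly treatment-emergent. A medication is wrongly dropped from the prior summary, and its concomitant status is unclear.

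Nothing else in the documents repairs this, since the onset precaution in the same section points the same way. The frequency is unknown and probably low. The effect is confined to treatment-emergent and prior/concomitant classification and the related listings; no efficacy result depends on it. This is a minor correction. The conclusion rests on applying the SAP text as written, without an unstated programming safeguard.

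**What to change.** Make two text changes in SAP 6.1.8, with matching program logic, before unblinding.

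1. In the day-missing branch, use the first-dose day only if month and year match and no recorded end date falls before the first-dose date; otherwise assign day 01.
2. In the adverse-event onset precaution, exempt events whose recorded end date is before first dose. Without this, the first change could be overridden and the event moved back to a post-dose onset.

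The wording in item 1 keeps an event that ended on Day 1 itself as possibly treatment-emergent, whereas the month-missing branch requires an end strictly after first dose. Choose one boundary and use it in both branches. It would also help to give medications one definition of concomitant across SAP 9.7 and the Listing 16.2.9.7 footnote.

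The cost is a few lines of SAP text and a small change to date derivation. No new data are needed, and records with no end date or an end after dosing are unchanged.

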### 6.1.9. Presentation of Cohorts and Treatments in Summaries

Study subjects and demographic summaries will be presented by cohort and treatment in the same output, as follows:

- Cohorts 1 and 2: Cohort 1 (ARQ-252 cream 0.3% QD); Cohort 2 (ARQ-252 cream 0.3% QD, ARQ-252 cream 0.3% BID, ARQ-252 cream 0.1% BID, vehicle cream QD, and vehicle cream BID)

Efficacy data will be presented separately for each cohort (where the efficacy parameter was collected for subjects in Cohort 1), as follows:

- Cohort 1: ARQ-252 cream 0.3% QD
- Cohort 2: ARQ-252 cream 0.3% QD, ARQ-252 cream 0.3% BID, ARQ-252 cream 0.1% BID, and vehicle cream (all dose frequencies)
- Cohort 2, Pooled Treatments: ARQ-252 cream (all strengths/dose frequencies), ARQ-252 cream 0.3% (all dose frequencies), and vehicle cream (all dose frequencies)

Safety summaries will be presented by cohort and treatment in the same output where possible, as follows:

- Cohorts 1 and 2: Cohort 1 (ARQ-252 cream 0.3% QD); Cohort 2 (ARQ-252 cream 0.3% QD, ARQ-252 cream 0.3% BID, ARQ-252 cream 0.1% BID, vehicle cream QD, and vehicle cream BID)

Otherwise, safety summaries will be presented separately for each cohort, as follows:

- Cohort 1: ARQ-252 cream 0.3% QD
- Cohort 2: ARQ-252 cream 0.3% QD, ARQ-252 cream 0.3% BID, ARQ-252 cream 0.1% BID, vehicle cream QD, and vehicle cream BID

## 6.2. Special Handling for COVID-19 Disruptions

In some cases, study visits will have to be delayed/not performed as a result of COVID-19 disruptions (e.g., sites were closed or subjects were under stay-at-home orders). Where possible, study sites may collect post-baseline data from subjects remotely by telephone, traditional mail, and/or email; this will be clearly documented in the source. If possible, sites should adhere to the protocol visit window for remote data collection.

Investigator assessments and subject questionnaires normally completed during on-site visits should be completed on the appropriate paper source documents. The following assessments/questionnaires are approved to be collected via telemedicine/remotely:

- WI-NRS
- Pain NRS
- Subject Local Tolerability
- QOLHEQ
- IP / diary compliance

The following assessments cannot be completed via telemedicine/remotely:

- IGA
- BSA
- Investigator Local Tolerability
- Subject Weight
- HECSI
- Nail Dystrophy Assessment

Study visits and procedures must be followed per protocol whenever possible. Any specific changes in study conduct that deviate from the protocol should be communicated to the institutional review board and Sponsor. All protocol deviations which occurred as a result of COVID-19 disruptions (e.g., visits out of window, missed assessments, etc.) will be differentiated from other protocol deviations.

## **7. STUDY SUBJECTS AND DEMOGRAPHICS**

Presentation of treatments for the study subjects and demographics summary tables are described in [Section 6.1.9](#).

### **7.1. Disposition of Subjects and Withdrawals**

Disposition will include tabulations of the number of subjects enrolled (Cohort 1) or randomized into each treatment group (Cohort 2), the number of subjects who received treatment, subjects completing the study, tabulated reasons for discontinuation from the study, including whether or not the subject did not complete the study due to COVID-19 disruption and reasons, and number of subjects in each analysis population. Disposition will be summarized for all subjects who were entered into the database by treatment group within cohort. This summary will be based on all enrolled (Cohort 1) or randomized (Cohort 2) subjects.

### **7.2. Protocol Violations and Deviations**

The number of subjects with important protocol deviations and/or eligibility deviations will be summarized in categories by treatment group within cohort for subjects in Safety population; the incidence of all protocol deviations will also be provided. All protocol deviations will be provided in the data listings.

### **7.3. Demographics and Other Baseline Characteristics**

Summary statistics for age, gender (including child-bearing potential), race, ethnicity, height, weight, percent BSA affected by disease (dorsal [left hand], dorsal [right hand], palmar [left hand], palmar [right hand], total hand), BMI, and baseline disease characteristics (IGA, WI-NRS, HECSI subscores and total score, Pain NRS, and QOLHEQ subscores and total score) will be presented by treatment group within cohort, as well as for overall subjects across both cohorts.

A summary of chronic hand eczema history, including primary morphologic subtype of hand eczema, patch test results, and distribution of chronic hand eczema (presence of eczema on each hand on the following surfaces: palmar [including lateral aspects of fingers], dorsal, interdigital, and pulpitis) will be presented by treatment group within cohort.

The number and percent of subjects reporting various medical histories, grouped by MedDRA system organ class and preferred term, will be tabulated by treatment group within cohort.

For the continuous variables, the number of nonmissing values and the mean, SD, minimum, median and maximum will be tabulated.

For ordinal variables such as the IGA, WI-NRS, and Pain NRS, summary statistics including the mean, median, and range of the ordinal variable will be presented, as well as frequency counts of each level of the ordinal variable.

For the categorical variables, the counts and proportions of each value will be tabulated.

These analyses will be conducted for the ITT and Safety populations, except for chronic hand eczema history summary, which will only be summarized on the Safety population.

#### **7.4. Exposure and Compliance**

The number of IP applications by each subject based on diary data will be summarized using descriptive statistics appropriate for continuous variables.

The amount of IP each subject used based on tube weight will be summarized descriptively by treatment group using continuous methods.

A subject will be considered compliant with the dosing regimen if the subject applies at least 80% of the expected applications during the IP application period and does not miss more than 3 consecutive days of dosing.

Investigational product application compliance will be calculated based on number of applications divided by the expected number of IP applications. Compliance will be summarized descriptively by treatment group using the following categories:

- >100%
- ≥80% - ≤100%
- <80%

### **8. EFFICACY ANALYSIS**

The statistical models described in this section apply to subjects in Cohort 2 (Phase 2b) only, unless otherwise specified. Presentation of treatments for the efficacy summary tables are described in [Section 6.1.9](#).

#### **8.1. Primary Efficacy Analysis**

##### **8.1.1. Investigator Global Assessment (IGA) Score of “Clear” or “Almost Clear” at Week 12**

The IGA is a static evaluation of qualitative overall chronic hand eczema severity. This global assessment scale is an ordinal scale with five severity grades (reported only in integers of 0 to 4). Each IGA Severity Score is defined by distinct and clinically relevant morphologic descriptions that minimizes inter-observer variability. [Table 7](#) illustrates the description of each severity grade.

**Table 7: IGA**

Score	Grade	Description
0	Clear	Absence of erythema and scaling, AND
		Absence of vesiculation, edema, and fissures. Note: Post-inflammatory pigmentary changes may be present.
1	Almost clear	Barely perceptible or faint erythema, and/or Slight flaking over limited areas, mostly fine scales, AND
		Absence of vesiculation, edema, or fissures
2	Mild	Barely perceptible or faint erythema, and/or Slight flaking over limited areas, mostly fine scales AND
		Scattered vesicles affecting up to 10% of hand, without erosion, and/or Dermal swelling over less than 10% of hands, and/or Cracked skin affecting a small area of the hand
3	Moderate	Either barely perceptible or faint erythema, or prominent redness, and/or Either slight flaking over limited areas, mostly fine scales, or flaking over widespread area(s), coarser scale AND
		Scattered or clustered vesicles affecting up to 30% of hand, without visible erosion or excoriation, and/or Definite dermal swelling over more than 10% of hand, and/or Cracked skin affecting multiple areas of the hand
4	Severe	Either prominent or deep intense red color, and/or Either flaking over widespread area(s), coarser scales, or desquamation covering over 30% of the hand, with coarse thick scales AND
		At least one of the following: High density of vesicles extending over large area(s), or with erosion or excoriation, and/or Dermal swelling with skin induration over widespread area(s), and/or One or more deep fissures and causing bleeding

### Categorical Data Analysis

The primary efficacy endpoint is the rate of subjects achieving an IGA score of “Clear” or “Almost Clear” at Week 12.

The primary statistical comparisons for Cohort 2 subjects will be as follows:

- ARQ-252 cream 0.3% BID versus vehicle cream (all dose frequencies)
- ARQ-252 cream 0.3% QD versus vehicle cream (all dose frequencies)
- ARQ-252 cream 0.1% QD versus vehicle cream (all dose frequencies)
- ARQ-252 cream (all strengths and dose frequencies) versus vehicle cream (all dose frequencies)
- ARQ-252 cream 0.3% (all dose frequencies) versus vehicle cream (all dose frequencies)

The primary endpoint will be analyzed using a CMH test stratified by pooled study site group and baseline IGA category. Statistical significance will be concluded at the 10% significance level (2-sided) or less, as discussed in [Section 4.1](#). Odds ratios and 90% and 95% CIs for the odds ratios will be provided. Additionally, the 90% and 95% Wilson CIs for proportion of successes in each treatment group will be presented.

For the primary analysis, missing IGA scores will be imputed using multiple imputation as described in [Section 6.1.4](#). These imputations will result in a minimum of 25 to a maximum of 250 complete analysis datasets, depending on the number of imputed monotone datasets required. The CMH analyses will be performed separately for each of the complete analysis data sets, and the results will be combined into one multiple imputation inference (estimated treatment effect and associated CI and *P* value).

The primary efficacy analysis will be based on Cohort 2 subjects in the ITT population.

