6.1.1 Determination of Sample Size

Cohort 1 will include approximately 6 evaluable subjects, which is deemed adequate for the purpose of evaluating safety and PK prior to Cohort 2.

There are approximately 215 subjects planned for Cohort 2. Approximately 61 subjects will receive ARQ-252 cream 0.3% QD, approximately 61 subjects will receive ARQ-252 cream 0.3% BID, approximately 31 subjects will receive ARQ-252 cream 0.1% QD, approximately 31 subjects will receive matching vehicle cream QD, and approximately 31 subjects will receive vehicle cream BID. The randomization scheme will be 2:2:1:1:1 between these 5 treatment groups, stratified by study site and IGA at Baseline.

The primary statistical comparisons will be to assess the ARQ-252 cream 0.3% group BID group versus the vehicle BID group, to assess the ARQ-252 cream 0.3% QC group versus the vehicle QD group, and to assess the ARQ-252 cream 0.1% QD group versus the vehicle QD group. A sample size of 55 per active arm and 28 per vehicle arm will provide approximately 85% power at the 2-sided 10% significance level to detect a difference in the rate of subjects attaining an IGA score of clear or almost clear (for each ARQ-252-treated group versus vehicle group within the same daily dosing frequency), assuming an active treatment response rate of 45% and a vehicle response rate of 15%. This is based on a 2-group X² test of equal proportions (without continuity correction). With a 10% dropout rate, the sample size for the study would be increased to 61 subjects per active arm and 31 subjects per vehicle arm (215 subjects total).

The primary statistical comparisons and evaluations of secondary endpoints will not be adjusted for multiplicity.

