### **3.2. Sample Size and Power**

Cohort 1 will include approximately 6 evaluable subjects, which is deemed adequate for the purpose of evaluating safety and PK before Cohort 2 commences.

There are approximately 215 subjects planned for Cohort 2. The primary statistical comparisons will be to assess the ARQ-252 cream 0.3% BID group versus the vehicle BID group, to assess the ARQ-252 cream 0.3% QD group versus the vehicle QD group, and to assess the ARQ-252 cream 0.1% QD group versus the vehicle QD group. A sample size of 55 per active arm and 28 per vehicle arm will provide approximately 85% power at the 2-sided 10% significance level to detect a difference in the rate of subjects attaining an IGA score of clear or almost clear (for each ARQ-252-treated group versus vehicle group within the same daily dosing frequency), assuming an active treatment response rate of 45% and a vehicle response rate of 15%. For testing each active arm of 55 subjects versus the combined vehicle arms of 56 subjects, this sample size provides over 90% power for the comparison of the rate of subjects attaining an IGA score of clear or almost clear. This is based on a 2-group X2 test of equal proportions (without continuity correction).

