### **3.4. Treatments Administered**

Cohort 1 will include approximately 6 evaluable subjects; all subjects are to receive ARQ-252 cream 0.3% QD.

Approximately 61 subjects will receive ARQ-252 cream 0.3% QD, approximately 61 subjects will receive ARQ-252 cream 0.3% BID, approximately 31 subjects will receive ARQ-252 cream 0.1% QD, approximately 31 subjects will receive matching vehicle cream QD, and approximately 31 subjects will receive vehicle cream BID. The randomization scheme will be 2:2:1:1:1 between these 5 treatment groups, stratified by study site and IGA at Baseline.

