#### 6.1.2. Adjustments for Covariates

Covariates for this study include pooled site group (see [Section 6.1.6](#)) and IGA severity at baseline (mild, moderate, or severe). Subgroup analyses may be generated for the baseline covariates.

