### 6.1.6. Pooling of Sites

Sites will be pooled for statistical analysis as follows. For analysis, sites should have a minimum of 10 randomized subjects. The smallest sites will be grouped sequentially in order of smallest to largest within each country, restricting to those sites that did not meet the minimum enrollment of 10, until each pooled site has a minimum of 10 subjects within each country with at least 1 subject in each treatment group.

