#### **8.1.2. Sensitivity Analyses of the Primary Efficacy Endpoint**

The following sensitivity analyses will be performed, based on the CMH test as described in [Section 8.1](#):

- The primary efficacy endpoint analysis, repeated on Cohort 2 subjects in the ITT and PP populations on nonimputed data; and
- The primary efficacy endpoint analysis (excluding the CMH testing), repeated on Cohort 1 subjects in the All Treated population on nonimputed data only.

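### The power stated in SAP 3.2 does not apply to the 0.1% QD comparison: the arm is about 31, not 55, and under the planned stratified CMH test its power is roughly 75-88%

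*SAP*

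**What the plan says.** SAP 3.2 gives the power for the pooled-vehicle comparisons: "For testing each active arm of 55 subjects versus the combined vehicle arms of 56 subjects, this sample size provides over 90% power". It names the method: "This is based on a 2-group X2 test of equal proportions (without continuity correction". The assumed rates are 45% on active and 15% on vehicle, at a two-sided 10% level.

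SAP 3.4 sizes the low-strength arm differently: "approximately 31 subjects will receive ARQ-252 cream 0.1% QD". That is half of each 0.3% arm, as the 2:2:1:1:1 ratio implies. Protocol 6.1.1 lists the five arm sizes correctly, but then says the sample size "would be increased to 61 subjects per active arm and 31 subjects per vehicle arm (215 subjects total".

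SAP 8.1.1 lists 0.1% QD versus pooled vehicle among the five primary comparisons and prescribes a CMH test: "The primary endpoint will be analyzed using a CMH test stratified by pooled study site group and baseline IGA category". Baseline IGA has three levels (SAP 6.1.2). Under SAP 6.1.6, small sites are grouped within country "until each pooled site has a minimum of 10 subjects within each country with at least 1 subject in each treatment group". SAP 8.1.2 offers this check for Cohort 2: "The primary efficacy endpoint analysis, repeated on Cohort 2 subjects in the ITT and PP populations on nonimputed data", again with the CMH of 8.1. No section gives power for an active arm of about 31, or for the stratified test.

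**The concern.** The stated power rests on two inputs that do not describe the 0.1% QD comparison.

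- **Arm size.** No 0.1% arm of 55 exists. The Protocol 6.1.1 sentence has the same slip: with three active and two vehicle arms, 3 x 61 + 2 x 31 = 245. Only 2 x 61 + 3 x 31 gives 215.
- **Test.** A CMH test draws information only from strata that contain both arms of the contrast and both outcomes. The pooling rule guarantees at least one subject per arm in a pooled site, but not in a pooled site split by IGA.

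0.1% QD is the only low-strength arm in a dose-ranging trial. A reader who trusts over 90% power would take a non-significant 0.1% result as fairly strong evidence that the low strength does not work. Both Cohort 2 sensitivity analyses keep the same strata, so neither would show whether sparse strata had cost the comparison its power.

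**Working it through.** **Inputs.** From the documents: 45% and 15%, two-sided alpha 0.10 (z = 1.645); 0.1% QD about 31; vehicle 31 + 31 = 62; 10% dropout, giving about 28 and 56; about 45 sites (Protocol 4.2); three IGA grades.

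**Step 1: the plan's own figure.** For the uncorrected two-group chi-square,

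power = Φ{ [ |p1 - p0| - z·√( p̄(1 - p̄)(1/n1 + 1/n0) ) ] / √( p1(1 - p1)/n1 + p0(1 - p0)/n0 ) },

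with p̄ the size-weighted mean rate.

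| n1 vs n0 | p̄ | null SE | alternative SE | argument of Φ | power |
|---|---|---|---|---|---|
| 55 vs 56 | 0.2986 | 0.0869 | 0.0823 | 1.908 | 97.2% |
| 31 vs 62 | 0.2500 | 0.0953 | 0.1002 | 1.430 | 92.4% |
| 28 vs 56 | 0.2500 | 0.1002 | 0.1054 | 1.282 | 90.0% |

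The first row reproduces the SAP claim. The other two give the real 0.1% QD sizes without and with dropout; exact enumeration gives 92.9% and 90.7%. Arm size alone therefore takes the power to the edge of the claim.

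**Step 2: how thin the strata are.** A pooled site of 10 holds on average 10 x 31/215 = 1.4 subjects on 0.1% QD and 10 x 62/215 = 2.9 on vehicle, before any split by IGA. In the main simulation the 6.1.6 rule gave on average 13.3-14.8 pooled sites and 34-41 non-empty strata. Between 15% and 35% of the subjects in this contrast sat in strata with only one of its two arms.

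**Step 3: power of the planned CMH.** The simulation used 215 subjects, 45 sites, 6.1.6 pooling within country and 3,000 runs per scenario (standard error about 0.7 points). For 0.1% QD versus pooled vehicle:

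| Analysis | No loss | 10% missing, observed only | 10% dropout, multiple imputation |
|---|---|---|---|
| Planned CMH, blocks of 7 within site x IGA | 83-88% | 77-83% | 82%, 85% |
| Planned CMH, unrestricted allocation | 80-85% | 74.5-82% | 78%, 84% |

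On the same simulated trials the unstratified test gave 90-94% and a CMH by baseline IGA alone 89-94% (89-93% with imputation). The imputation column comes from 1,000 runs in each of four scenarios (standard error about 1.2 points), using predictive mean matching, 25 imputations and Wilson-Hilferty combination. Non-monotone missing data were not simulated.

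The documents do not fix these inputs, so they were assumed: block size; gamma site sizes (shape 1 or 3); 32/8/5 sites by country; IGA mix 20/60/20 or 10/80/10 (the 20% figures are only caps); log-odds change per IGA grade 0.7 or 0; site SD 0, 0.4 or 0.8; and merging a leftover small pool into the last pool of its country.

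**Step 4: checks.**

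- Rejection under the null was 9.5-10.6% for the planned CMH, and 8% in the one null scenario with imputation.
- A second simulation with other country splits and stratum effects, blocked allocation and 2,500 runs per scenario gave 83.2-89.2% with no loss and 77.6-84.9% with 10% missing.
- Fixing the number of pooled sites instead gave 84-91% with 6 pools, 80-89% with 10, 72-86% with 15 and 66-82% with 20.

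**Step 5: the other primary comparisons under the planned CMH.** In the main simulation, single 0.3% arms kept 92-97% (blocked) or 90-96% (unrestricted); 0.3% QD with imputation had 91-95%. The two pooled-active comparisons kept 97% or more.

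**The case against.** The strongest reply is that the documented slip hardly moves the number. The primary analysis is ITT with imputation, so the matching unstratified size is 31 versus 62, and 92.4% is still over 90%. That is right, and it means the shortfall needs the stratification as well as the small arm.

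The stratified figures rest on inputs the documents do not give, and with as few as 6 pooled sites the power could reach 91%. This also stands, and is why the result is a range. The lowest values combine unrestricted allocation with observed-only data, which is not the primary analysis. The nearest runs to the plan (blocked, imputed) gave 82% and 85%. All four imputed runs were nevertheless below 90%.

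SAP 3.2 discloses that it used an unstratified test, a common planning approximation. For the 0.3% arms that approximation does little harm. For an arm half the assumed size it does.

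Over-reading of a null result is partly guarded against by the odds ratio intervals and per-arm Wilson intervals. The Wilson intervals are unstratified, so crude rates will be visible. They are not a between-arm comparison, however, and the shell for Table 14.2.1.1.1 takes the proportions from observed data while the odds ratio uses imputed data.

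Finally, an IGA-only CMH drops a randomization factor and adds a p-value where multiplicity is not controlled. That is a fair caution, and a reason to keep it strictly as a sensitivity analysis.

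**Conclusion.** The concern holds. Over 90% power is correct for 55 versus 56 with an unstratified test, but it is not what the plan delivers for 0.1% QD. Under the planned CMH the power is roughly 75-88%, so the chance of missing a true 45% versus 15% effect is roughly 12-25%, against under 10% as stated. The range rests on about 45 sites and the allocation, site-size, IGA and missing-data assumptions listed above; confidence in its exact limits is moderate. It also takes the plan's 45% as true for the low strength, and a lower rate would reduce power further. The 0.3% arms are borderline at worst and the pooled-active comparisons are unaffected. The problem is a misstated power and a risk of over-reading one null result, without inflation of type I error. It is worth correcting but does not threaten the trial.

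**What to change.** 1. In SAP 3.2, restate power for each of the five comparisons in 8.1.1 under the stratified CMH, with 0.1% QD at 31 (28 after dropout). Suitable wording: under the CMH test stratified by pooled site group and baseline IGA category, power is roughly 75-88% for 0.1% QD, 90-97% for each 0.3% arm and at least 97% for the two pooled-active comparisons. Follow this with the assumptions on allocation method, site sizes, IGA mix, IGA effect and dropout. The sponsor knows the block size and site enrolment and can narrow the range.
2. In SAP 8.1.2, add one CMH for Cohort 2, ITT, on the same imputed datasets, stratified by baseline IGA only. Label it as a sensitivity analysis, since it does not adjust for site. The primary test stays as planned.
3. As a wording alignment only, say pooled site group where 6.1.4 step 3 says site. SAP 6.1.2 already reads "Covariates for this study include pooled site group", and 8.1.1 agrees.

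The cost is SAP text and one additional table, before unblinding. No extra subjects or data are needed.
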